5.2.2 Inflammatory Markers

Markers of inflammation are elevated with aging and their increase has been associated with cognitive decline [27, 28]. Epidemiological and retrospective data reveals an improvement in neurocognitive function with the use of NSAIDs in patients with Alzheimer's dementia, supporting an inflammatory process involved in neurocognitive decline [23]. Chronic inflammation as a result of mass effect from tumor or treatment related inflammation may be associated with neurocognitive deficits and can be measured in plasma. Interleukin 1 (IL-1), Interleukin 6 (IL-6), and Tumor Necrosis Factor alpha are pro-inflammatory cytokines that are a measure of inflammation and have been shown to be elevated in patients with Alzheimer's dementia [29-32]. In this study, inflammatory biomarkers will be measured at baseline (after registration, but prior to treatment) and at each follow-up visit when neurocognitive testing is performed.

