5.2.3 Hormone and Growth Factors

Aging and memory decline is associated with the disruption of hormone regulation, including glucocorticoids, gonadal steroids, and growth hormone [33]. Cortisol, human chorionic gonadotropin (hCG), insulin-like growth factor-1

(IGF-1), and neuronal growth factor (NGF), have all recently been associated with cognitive decline in Alzheimer's disease [34, 35]. ELISA testing of serum specimens for each hormone and growth factor will be performed at baseline (after registration, but prior to treatment) and at each follow-up visit when neurocognitive testing is performed.

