9.0 Evaluation During Study

- 9.1 A history and physical exam will be performed at two month intervals for a total of 24 months of follow up after the completion of the assigned treatment (±30 days). Note the first evaluation after radiotherapy will frequently be performed approximately 4 weeks after completion of radiotherapy and then the study will continue with history and physical exam at 2 month intervals.
- 9.2 Neuropsychological testing will be performed at each follow up visit, up to two years post radiation treatment. Reasonable effort will be made to complete this testing prior to patients meeting with their physicians and receiving information about the status of their disease.
- 9.3 Routine MR imaging of the brain performed with and without contrast will be obtained at each follow up visit at 2 month intervals (±30 days) until recurrence or up to two years post radiation treatment. Note the first evaluation after radiotherapy will frequently be performed approximately 4 weeks after completion of radiotherapy and then the study would continue with follow-up imaging at 2 month intervals. These post-treatment scans will be analyzed and compared to baseline scans for identification of regions demonstrating changes in contrast enhancement including size, heterogeneity and rim thickness. Qualitative estimation of associated T2-FLAIR changes will also be evaluated. Early stages of malignant gliomas have demonstrated decreased water diffusion. Routinely obtained diffusion weighted images and reconstructed ADC maps will be analyzed to see if there is a difference between pre- and various post-treatment scans. Based on contrast enhancing imaging features, manually selected regions of interest on ADC maps will be

quantitatively analyzed, normalized to contralateral unaffected brain parenchyma and compared on serial scans. Similarly DTI maps and cognitive functions will be correlated.

- 9.4 Medication usage (specifically steroid dose, narcotic pain medications, antiepileptic agents, psychostimulants) will be recorded. Steroid doses will be adjusted based on clinical and radiographic criteria.
- 9.5 Requirements for more frequent evaluation will be documented. Data on unscheduled follow-ups will also be documented.

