- 9.6 Research blood products will be collected within the first five fractions of treatment and at each evaluation period as stated above. At each interval, 2 tubes (10 mL) of serum (using "red" top tube, no additive) and 1 tube (10 mL) of whole blood (EDTA additive, "purple" top tube) will be collected.

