 - 10.3.2 Inflammatory Markers: Serum specimens collected within the first five fractions of treatment and at each follow-up visit will be analyzed using commercially-available ELISAs from R&D Systems, Inc. for the following inflammatory biomarkers: interleukin 1 (IL-1), interleukin 6 (IL-6), and tumor necrosis factor alpha (TNFα). These markers will be assayed in the laboratory of the Study Chair.
 - 10.3.3 Hormone and Growth Factors: Serum specimens collected within the first five fractions of treatment and at each follow-up visit will be analyzed using commercially available Enzyme Linked Immunosorbant Assays (ELISAs) for the following hormone and growth factors: glucocorticoids (e.g., cortisol), gonadal steroids (e.g.,

estradiol, testosterone, progesterone), growth hormone, human chorionic gonadotropin (hCG), insulin-like growth factor-1 (IGF-1), and neuronal growth factor (NGF). These assays will be performed in the laboratory of the Study Chair.

- 10.3.4 A portion of the serum and DNA will initially be analyzed as described above. According to patient consent information, the remaining body fluid biospecimens will be stored as de-identified frozen specimens in locked storage at -70°C in the laboratory of the Study Chair. As new protocols are developed they will be presented for IRB review and approval.
- 10.3.5 Return of Genetic Testing Research Results: Because the results generated by the genetic testing included in this section are not currently anticipated to have clinical relevance to the patient or their family members, the genetic results will not be disclosed to the patients or their physicians. If at any time, genetic results are obtained that may have clinical relevance, IRB review and approval will be sought regarding the most appropriate manner of disclosure and whether or not validation in a Food and Drug Administration (FDA) Clinical Laboratory Improvement Amendments (CLIA)-certified setting will be required. Sharing of research data with individual patients should only occur when data have been validated by multiple studies and testing has been done in CLIA-approved laboratories.

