We will use descriptive statistics to summarize by treatment arm the quality of life data at each assessment time. We will also use boxplots to summarize the quality of life data by treatment arm at each assessment time. We will model the quality of life data using mixed effects regression methods with repeated measures. The model will include treatment arm, selected dosimetric parameters, baseline cognitive function, location of the primary tumor (left vs. right hemisphere, if bilateral disease is present, location will be determined by the hemisphere with highest burden of disease), and the stratification factors used at randomization as fixed effects and patient as a random effect. We will similarly analyze the cognitive tests. For nearly all the prior mentioned analyses we will also plan to conduct an as-treated analysis.

We will tabulate by treatment arm the adverse events by grade and relationship to treatment.

We will use logistic regression methods to model the logit of the probability of neurocognitive decline as function of ApoE (i.e., Apo E2, Apo E3, Apo E4) genotyping, inflammatory markers (i.e., IL-1, IL-6, TNF- α), and hormone growth factors (i.e., glucocorticoids, gonadal steroids, growth hormone, human chorionic gonadotrpin, insulin-like growth factor-1, neuronal growth factor).

Determination of MCP class will be determined by RPA analysis using results of MGMT, *IDH1*, G-CIMP, and mRNA assays as well as RTOG RPA class. We will use descriptive statistics to report class distributions overall and by treatment arm. Survival by classes will be visualized on Kaplan/Meier plots, compared by the logrank test. The Cox proportional hazards regression will be used to model MCP classification, adjusting for treatment arm and stratification factors.

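### Serum markers are assayed at every visit, but section 12.4 gives only a logistic model with no time index, so no specified analysis uses the serial values

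*Combined protocol and SAP*

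**What the plan says.** **Sampling.** Section 5.2.2 states that "inflammatory biomarkers will be measured at baseline (after registration, but prior to treatment) and at each follow-up visit when neurocognitive testing is performed". Section 5.2.3 gives hormones and growth factors the same schedule: testing is "performed at baseline (after registration, but prior to treatment) and at each follow-up visit when neurocognitive testing is performed". The operational sections place the first draw differently. Section 9.6 says "Research blood products will be collected within the first five fractions of treatment and at each evaluation period as stated above", and sections 10.3.2 and 10.3.3 say "Serum specimens collected within the first five fractions of treatment and at each follow-up visit will be analyzed". The serial specimens are thus to be assayed and not only stored. On visit timing, section 9.1 says "A history and physical exam will be performed at two month intervals for a total of 24 months of follow up", and section 9.2 puts cognitive testing at each of those visits.

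**Purpose.** Objectives 3.3.2 and 3.3.3 ask whether the markers predict radiation-induced cognitive decline. As part of the rationale, section 5.2.2 says that "treatment related inflammation may be associated with neurocognitive deficits and can be measured in plasma".

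**Analysis.** Section 12.4 says "We will use logistic regression methods to model the logit of the probability of neurocognitive decline as function of ApoE" and then lists the inflammatory markers and the hormones and growth factors. For quality of life, the same section says "We will model the quality of life data using mixed effects regression methods with repeated measures", with patient as a random effect, and it extends that approach to the cognitive tests. It does not extend it to the markers.

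**The concern.** The data are longitudinal, but the stated model has no place for time. As written, it does not say which draw enters, whether the value is absolute or a change, when decline is assessed, how repeated values from one patient are handled, or whether treatment arm is included.

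Three things follow.

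- If the analyst takes the first value, the follow-up assays go unused. A mechanism that arises during or after radiotherapy is then largely out of view, because that sample precedes treatment or barely overlaps it.
- Testing and blood draws continue to two years, so a patient who fails early goes on giving samples. Nothing stops a value drawn at or after the failure from being used to predict it.
- A plain yes/no outcome gives no defined place to patients who progress or die before cognitive failure. Sections 10.1.1 and 12.3 treat these as competing events for the primary endpoint.

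At stake is what can be learned about objectives 3.3.2 and 3.3.3 from serial samples the trial already pays for. Without a rule, the draw or summary could also be chosen after the data are seen, across 11 markers.

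**Working it through.** **1. The plan's own figure.** No power or event figure is given for the marker analysis. The only design figure to reproduce is the 43 events for the primary comparison (section 12.2).

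- Hazards: -ln(0.55)/4 = 0.1495 and -ln(0.70)/4 = 0.0892 per month, so HR = 0.597.
- Events (Schoenfeld, one-sided 0.20, 80% power): 4 × (0.8416 + 0.8416)² / (ln 0.597)² = 11.33 / 0.267 = 42.5, rounded up to 43. This agrees with the plan.

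**2. Draws per patient.** 24 / 2 = 12 follow-up visits plus the first draw = 13, or 14 if the visit at about 4 weeks is additional.

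**3. Model size.** Section 3.3 names 3 cytokines and 8 hormones or growth factors (cortisol, estradiol, testosterone, progesterone, growth hormone, hCG, IGF-1, NGF), which makes 11 serum markers.

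- Every draw as its own covariate: 11 × 13 = 143 terms for 60 to 90 patients, which is not feasible.
- One value per marker plus 2 df for ApoE: 13 df. Section 12.4 does not define decline. If it means the primary event, 60 evaluable patients give 43 events and 17 non-events, and 17 / 13 = 1.3 per df in the smaller class.

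An analysis with one row per patient therefore needs a chosen draw or summary, and even then the markers cannot sensibly be fitted together.

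**4. What a visit-level model would gain.** The documents give no effect size or marker correlation, so this is an illustration. Inputs:

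- 60 evaluable patients (12.2), visits every 2 months to 24 months (9.1).
- Assumed: 22% failure per visit, so 1 - 0.78² = 39% by 4 months, between the plan's 30% and 45%.
- Exit from the 27.2% two-year survival cited in section 4.0: 1 - 0.272^(1/12) = 10.3% per visit. As progression also ends follow-up for this purpose and the documents give no rate, an assumed 8-month median exit was run too: 1 - 0.5^(1/4) = 15.9% per visit.
- Assumed: true odds ratio 1.65 per SD of the marker at the preceding visit; within-patient marker correlation 0.3 to 0.7; one marker; two-sided 0.05.

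| Analysis | Power, exit from survival only | Power, 8-month median exit |
|---|---|---|
| Ever-declined on first value | 15-24% | 11-24% |
| First failure on preceding-visit value | 75-77% | 67% |
| First failure on baseline plus change, joint 2-df test | 66-70% | 56-57% |

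Type I error was about 4-6%. Separate runs of the survival-exit scenario put first-value power anywhere from 9% to 29%. A repeat with exit applied before each visit's test and a linear visit term came out up to about five points lower on the last two rows. The ordering and the size of the gap were stable.

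**5. Per-patient summaries.** In one such run, with correlation 0.3 / 0.5 / 0.7, the mean over visits gave 21 / 27 / 36% power and the last value 9 / 12 / 23%, against 80 / 76 / 79% for the preceding-visit value.

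**The case against.** The strongest reply is that the plan is silent, not wrong. Its reference to logistic regression methods leaves room for a landmark value, a change from baseline, a per-patient mean, GEE or a mixed logistic model. The discrete-time model recommended here is itself a logistic regression. This stands. A reader might infer that the serial values must be either discarded or counted as independent, but the documents do not commit to either.

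Pooling would indeed be harmful. If an ever/never outcome were copied to 13 rows per patient, the design effect would be 1 + 12 × 0.3 = 4.6 to 1 + 12 × 0.7 = 9.4, and a nominal 5% test would reject in about 36-53% of null trials. But that describes an analysis the plan never states.

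A reader might also infer that treatment-related inflammation cannot be tested. That goes too far: a post-treatment or change value would fit the stated model. The objectives ask only about prediction, and section 5.2.2 offers treatment-related inflammation as one of two alternative sources, alongside mass effect from tumor.

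Three technical cautions also stand.

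- In a baseline-plus-change model, the change term alone had 58% / 38% power at correlation 0.3 / 0.7, so the higher figures must not be credited to it.
- With strong unmeasured differences between patients (random intercept SD 2), the preceding-visit model's type I error rose to 6.4% / 10.5% at those correlations.
- With 11 markers entered jointly, the change term's null rejection was 8-9%.

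Finally, these are exploratory objectives with no alpha or decision attached. That limits the weight of the point. It does not supply an analysis for the serial data.

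**Conclusion.** The point holds in this form: the serial marker values have no specified analysis, and the one sentence in section 12.4 does not prevent values drawn at or after decline from acting as predictors. The plan's silence supports nothing stronger.

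If the current marker level drives decline, power for one marker is about 10-25% with the first value only, about 67-77% with the preceding-visit value and about 56-70% with the joint baseline-plus-change test, depending on exit rate. These figures rest on the assumed odds ratio of 1.65, correlation of 0.3-0.7 and 22% failure per visit, none of which is in the documents. If only the first-draw level matters, there is no gain. ApoE is fixed and is not affected, nor is the primary endpoint. The change is worth making because it uses data already planned, but it is not essential to the trial's main conclusion.

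**What to change.** In section 12.4, for the serum markers only:

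- Replace the logistic model with a discrete-time logistic model of first cognitive failure at visit k on the marker at visit k-1, among patients still free of failure, progression and death, with a visit term. State whether treatment arm and the stratification factors are included.
- Fit one marker at a time, given 11 markers against 43 expected events, and label the results exploratory. With 11 tests at 0.05, 11 × 0.05 = 0.55 false positives are expected if no marker matters.
- Report the first-draw value separately as the early predictor.
- If baseline plus change is used, test the two terms jointly. First reconcile sections 5.2.2 and 5.2.3, which put the first draw before treatment, with sections 9.6, 10.3.2 and 10.3.3, which allow it within the first five fractions. Change from baseline cannot be read until this is settled.
- A repeated-measures model of cognitive scores on the preceding marker value, with patient as a random effect, may be added. It has a different outcome, risk set and estimand, so it should be listed as a separate analysis and not as an equivalent.

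The cost is SAP wording and more analysis work. Samples, assays, cognitive tests and imaging are already scheduled. Some visits will lack a preceding sample and will drop out of the model.

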3.0 Objectives

3.1 Primary Objectives

- 3.1.1 To assess whether treatment with IMPT results in longer time to cognitive failure compared with IMRT. Cognitive failure is defined as the first cognitive failure on any of the following six cognitive outcome variables: Hopkins Verbal Learning Test Revised (HVLT-R) Total Recall, HVLT-R Delayed Recall, HVLT-R Delayed Recognition, Controlled Oral Word Association (COWA), Trail Making Test (TMT) Part A or Part B.
- 3.2 Secondary Objectives
 - 3.2.1 To determine local control in the brain post radiation treatment.
 - 3.2.2 To determine overall survival in each treatment arm.
 - 3.2.3 To assess quality of life measured at two month intervals for a total of two years post-radiotherapy for both treatment arms.
 - 3.2.4 To assess the pattern of cognitive change in memory at two month intervals for two years post-treatment as well as executive function and processing speed.
 - 3.2.5 MRI diffusion weighted images (DWI) and reconstructed apparent diffusion coefficient (ADC) maps will be analyzed to see if there is a difference between pre- and post-treatment scans. These will also be analyzed for differences between the two treatment modalities.
 - 3.2.6 To evaluate if diffusion tensor imaging (DTI) correlates to the cognitive changes and if there are differences between the two treatment modalities.
 - 3.2.7 To assess the pre-treatment factors of recursive partitioning analysis (RPA) class and mini mental status examination (MMSE) in the predictive determination of local and distant control and cognitive outcome in each treatment arm.
 - 3.2.8 To assess the correlation between location of primary lesion, total volume of intracranial disease, and cognitive outcome in each treatment arm.
 - 3.2.9 To determine the relationship between MGMT promoter methylation status and cognitive and local control outcomes.
 - 3.2.10 To document and descriptively compare post-treatment adverse side effects between the two treatment arms.
 - 3.2.11 To determine the relation between dosimetric parameters and cognitive and local control outcomes.
- 3.3 Correlative objectives
 - 3.3.1 To determine if Apo E (i.e., Apo E2, Apo E3, and Apo E4) genotyping may prove to be a predictor of radiation induced neurocognitive decline (or neuro-protection).
 - 3.3.2 To determine if inflammatory markers (i.e., IL-1, IL-6, and TNF- α) may prove to be predictors of radiation induced neurocognitive decline.

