10.0 Criteria for Response and Toxicity

10.1 Definition of primary endpoint:

- 10.1.1 Time to cognitive failure on any of the 6 primary variables from the pre-specified cognitive tests (HVLT-R total recall, HVLT-R delayed recall, HVLT-R delayed recognition, TMT Part A or Part B, COWA) with failure defined as a decline that meets or exceeds the reliable change index (RCI) for each cognitive test variable. A cumulative incidence approach will be used to estimate median time to cognitive failure in order to account for the competing risks of disease progression and death. Patients experiencing disease progression or patients that died prior to experiencing cognitive failure will be considered as having had a competing event. Progressive disease frequently causes cognitive decline, and the goal of this study is to assess the impact of the radiation treatment itself on cognitive decline.
- 10.2 Definitions of secondary endpoints:
 - 10.2.1 Local control and distant control in the brain will be measured by contrast-enhanced brain MRI scan using Response Assessment in Neuro-Oncology (RANO)Criteria, as follows [50].
 - 10.2.1.1 Complete Response (CR): Requires all of the following 1) complete disappearance of all enhancing measurable and non-measurable disease sustained for a minimum of 4 weeks; 2) no new lesions; 3) stable or improving nonenhancing (T2/FLAIR) lesions; 4) patients must be off corticosteroids (or on physiologic replacement doses only); and 5) stable or improved clinically.
 - 10.2.1.2 Partial Response (PR): Requires all of the following: 1) ≥50% decrease compared with baseline in the sum of products of perpendicular diameters of all measurable enhancing lesions sustained for at least 4 weeks; 2) no progression of non-measurable disease; 3) no new lesions; 4) stable or improved non-enhancing (T2/FLAIR) lesions on the same

or lower dose of corticosteroids compared with the baseline scan; 5) stable or improved clinically.

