- 10.2.4 At each two month interval follow up visit out to 2 years all six prespecified cognitive test variables will be assessed. The pattern of cognitive change in memory, executive function, and processing speed will be assessed at each time point. The composite cognitive function

score will be determined by averaging standardized Z-scores from all pre-specified cognitive test variables (5 out of 6 are required to calculate a composite score).

- 10.2.5 MRI imaging including diffusion weighted images (DWI) and reconstructed apparent diffusion coefficient (ADC) maps will be analyzed for differences between pre- and post-treatment scans. They will also be analyzed for differences between the two treatment modalities.
- 10.2.6 Diffusion tensor imaging (DTI) will be analyzed for correlation to the cognitive changes and for differences between the two treatment modalities.
- 10.2.7 Pre-treatment factors of RPA class and MMSE will be assessed for predictive determination of local and distant control and cognitive outcome in each treatment arm.
- 10.2.8 Assessment will be made for correlation between location of primary lesion, total volume of intracranial disease, and cognitive outcome for each of the treatment arms.
- 10.2.9 The relationship between MGMT promoter methylation status and cognitive and local control outcomes will be assessed.
- 10.2.10 Post treatment side effects will be recorded at each follow up visit out to two years. Toxicity will be recorded according the Common Terminology Criteria for Adverse Events v4.0.3 for Nervous System Disorders. Only grade 3 and above toxicity that is directly related to therapy will be required to be documented. Pretreatment symptoms should not be considered as toxicity related to the treatment and are not required to be documented unless the symptoms worsen as a result of therapy.
- 10.2.11 Dosimetric parameters such as dose to the hippocampus will be analyzed for relationship with cognitive and local control outcomes.
- 10.3 Evaluation of correlative markers
 - 10.3.1 Genetic markers: DNA will be extracted within the first five fractions of treatment in the laboratory of the Study Chair. Apo E (i.e., Apo E2, Apo E3, and Apo E4) genes will be analyzed for single nucleotide polymorphisms (SNPs) either by Taqman or direct sequencing.

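### The marker objectives are tested only by logistic regression on a yes/no decline, although a continuous composite score and a mixed model for the cognitive tests are already planned

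*Combined protocol and SAP*

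**What the plan says.** Objectives 3.3.1 to 3.3.3 ask whether ApoE genotype, inflammatory markers, and hormones and growth factors predict cognitive decline after radiation. The only analysis that section 12.4 gives for them is: "We will use logistic regression methods to model the logit of the probability of neurocognitive decline as function of ApoE", followed by the other two marker groups. It does not say how decline is defined for this model, at which visit or within what window, or at what significance level.

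The same document provides for richer data and a richer model:

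- **Testing (9.2):** "Neuropsychological testing will be performed at each follow up visit, up to two years post radiation treatment". Visits are about two months apart.
- **Composite score (10.2.4):** a continuous score obtained by "averaging standardized Z-scores from all pre-specified cognitive test variables", with at least five of the six required.
- **Mixed model (12.4):** "We will model the quality of life data using mixed effects regression methods with repeated measures". The cognitive tests are to be analysed in the same way. The listed fixed effects are arm, dosimetric parameters, baseline cognitive function, tumour side and the stratification factors. No marker is listed.
- **Marker sampling (5.2.2):** "inflammatory biomarkers will be measured at baseline (after registration, but prior to treatment) and at each follow-up visit when neurocognitive testing is performed".

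The one threshold for decline in the document belongs to the primary endpoint in 10.1.1: "failure defined as a decline that meets or exceeds the reliable change index (RCI) for each cognitive test variable", on any of six variables. Section 12.4 does not say that the marker model uses it.

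**The concern.** A binary outcome puts a patient who fell just short of the cut in the same class as one who improved, and a patient just past the cut in the same class as one who declined severely. Information on the size of the change is lost. The marker objectives rest on about 60 evaluable patients, so there is little to spare. The scores and the model that would keep this information are already in the plan, but the markers are not connected to them, and no reason is given for using only the binary outcome.

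**Working it through.** **The plan's own figure (12.2).** No power is stated for the marker models, so the figure to reproduce is the one for the primary comparison. Under exponential times the hazard ratio is ln(0.70)/ln(0.55) = 0.597. At one-sided 0.20 and 80% power, events = 4 × (0.842 + 0.842)² / (ln 0.597)² = 42.5, rounded up to 43. The plan's 43 events reproduce.

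**Event rates used below.** 30% and 45% are the plan's four-month failure rates, 37.5% is their mean, and 43/60 = 72% is the proportion expected to have failed by the time of analysis.

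**Information kept after one cut of a normal score.** E = φ(z)² / [p(1 − p)], where z is the normal quantile at event rate p.

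| p | φ(z) | p(1 − p) | E | Loss | 60 × E |
|---|---|---|---|---|---|
| 0.30 | 0.348 | 0.210 | 0.576 | 42% | 34.5 |
| 0.375 | 0.379 | 0.234 | 0.613 | 39% | 36.8 |
| 0.45 | 0.396 | 0.248 | 0.633 | 37% | 38.0 |
| 0.717 | 0.338 | 0.203 | 0.564 | 44% | 33.9 |

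Sixty patients analysed as yes/no carry the information of about 34 to 38 analysed on the continuous score. This does not depend on alpha.

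**Power.** Assumptions not in the documents: one continuous marker, one follow-up value per patient, n = 60, and a marker-outcome correlation r of 0.25 to 0.35. The non-centrality is d = atanh(r) × √(60 − 3), which gives 1.928, 2.337 and 2.759. Power is Φ(d − z_α) for the continuous score and Φ(d√E − z_α) after the cut, with z_α = 1.960 (two-sided 0.05) or 0.842 (one-sided 0.20). For example, at r = 0.30, p = 0.375 and two-sided 0.05:

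- continuous: Φ(2.337 − 1.960) = 65%
- binary: Φ(2.337 × √0.613 − 1.960) = Φ(−0.13) = 45%

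Ranges below run over the four event rates.

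| Alpha | r | Continuous | Binary | Points lost |
|---|---|---|---|---|
| two-sided 0.05 | 0.25 | 48.7% | 30.5-33.5% | 15.2-18.3 |
| | 0.30 | 64.7% | 41.9-46.0% | 18.7-22.8 |
| | 0.35 | 78.8% | 54.5-59.3% | 19.5-24.3 |
| one-sided 0.20 | 0.25 | 86.1% | 72.8-75.6% | 10.6-13.3 |
| | 0.30 | 93.3% | 82.0-84.6% | 8.7-11.3 |
| | 0.35 | 97.2% | 89.1-91.2% | 6.0-8.2 |

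Simulation at n = 60 and two-sided 0.05 (linear test against logistic likelihood-ratio test) gave losses of 15-24 points for a continuous marker and 13-28 for a binary marker with 25% prevalence, the nearer analogue of an ApoE carrier status.

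**What the calculation leaves out.** It covers one cut of one score. An illustrative one-visit simulation of the any-of-six rule assumed correlations of 0.3-0.7 between tests, a cut at 1.645 SD, a marker acting equally on all tests and two-sided 0.05. Power fell from about 77% for the composite to about 38-40%. Repeated visits would change the figures again.

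**The case against.** The strongest defence is that the objectives ask about predictors of decline, so modelling the probability of decline answers the question as posed. A thresholded decline is also the primary endpoint (10.1.1), and the cognitive scores are analysed continuously elsewhere in 12.4. This stands in part. It justifies keeping the logistic model and rules out saying that only the markers are dichotomised. It does not explain why the markers are left out of the continuous model, since decline is also a quantity.

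Second, the power figures depend on alpha. The only level in the document is one-sided 0.20, set in 12.2 for the primary comparison and not for these models. This stands, so both scenarios are shown and neither can be given as the trial's figure.

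Third, a reader might infer that a real marker effect would probably be missed. The documents do not support that. At one-sided 0.20 the binary analysis still has about 73-91% power in these cases. At two-sided 0.05 the continuous analysis itself has only about 49% at r = 0.25. Small numbers drive much of the risk, and the plan claims no power for the correlative objectives.

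Fourth, a reader might infer one binary outcome per patient. Section 12.4 gives no visit or window and does not exclude a per-visit model. The lack of a definition is itself a gap.

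Finally, the calculation is simpler than the trial: ApoE is a genotype, and 72% is a cumulative rate set against a single follow-up value. The direction survives, but the exact figures are illustrative.

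**Conclusion.** The point holds as an inefficiency in a correlative analysis. It does not touch the primary analysis. The marker objectives rest on a binary outcome alone, although a continuous composite and a suitable model are already planned. The loss of about 37-44% of the information is firm for one normal score cut once at the plan's event rates. The power cost is conditional on n = 60, r of 0.25 to 0.35 and one value per patient: about 15-24 points at an assumed two-sided 0.05, about 6-13 at one-sided 0.20. An unconditional loss of 15 to 25 points would overstate what the documents support. The any-of-six result suggests that the loss could be larger, but its correlations and cut are assumed, so it is not an estimate for this trial.

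**What to change.** In 12.4, make the main marker analysis the mixed model already planned for the cognitive tests:

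- **Outcome:** the composite Z-score of 10.2.4, adjusted for the baseline score.
- **Predictor:** the baseline marker and its interaction with time. Time is not among the listed fixed effects, so it has to be added. Say which sample counts as baseline, because 5.2.2 places it before treatment while 9.6 and 10.3.2 allow the first five fractions.
- **Visits:** those before progression, to match the aim in 10.1.1 of isolating the effect of radiation. State the assumption made about dropout at progression or death.
- **Alpha:** state the level and whether the test is one- or two-sided.

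Keep the logistic model as a companion, using the reliable-change definition of 10.1.1 and a stated time window.

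The cost is SAP wording and a little analysis time, with no new data. The downside is that the main result becomes a mean change per unit of marker, which is less directly clinical than a probability of decline. The companion model covers that.
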